No known side effects. However, Oral Impact® is unsuitable for people with cow's milk protein allergy and those who are severely septic. Oral Impact® should not be mixed with medication and food.

STUDY DESIGN

This will be a single-centre, non-randomised, interventional pilot study where people on haemodialysis will receive an immuno-nutrition supplement (Oral Impact®, Nestle) for 6 weeks.

STUDY CONFIGURATION

Primary outcome

Change in C reactive protein (CRP), and pro- and anti-inflammatory cytokine levels (via multiplex plasma analysis) after 6 weeks of treatment with an immuno-nutrition supplement.

Secondary endpoints

Change after 6 weeks of treatment with an immuno-nutrition supplement in:

- Biochemical blood variables including haemoglobin, urea, creatinine, potassium, phosphate, calcium, sodium, albumin, total proteins, total cholesterol and triglycerides.
- Body composition assessed with bioelectrical impedance analysis and BMI.
- Dietary intake assessed with 3-day food diaries.
- Muscle strength assessed with handgrip strength (HGS).
- SAF levels.

Safety endpoints

- AEs that occur will be reported during the study.
- Participant reported tolerability of the immuno-nutrition supplement.
- Monitoring of pre-dialysis serum potassium levels.

STUDY MANAGEMENT

The Chief Investigator (CI) has overall responsibility for the study and shall oversee all study management. The study will be co-ordinated from the University of Nottingham campus at the Royal Derby Hospital. Data will be collected at the Renal Dialysis Unit of the Department of Renal Medicine at the Royal Derby Hospital (University Hospitals of Derby and Burton NHS Foundation Trust) and stored at the University of Nottingham.

The CI and Co-investigators are responsible for study planning, recruitment, consenting, data collection, handling and interpretation. The data custodian will be the CI, [name].

DURATION OF THE STUDY AND PARTICIPANT INVOLVEMENT

Participant recruitment will begin in January 2022 once all necessary approvals are in place, with an anticipated total recruitment and intervention delivery period of 3 months (i.e., end of March 2022). The study will end when the last participant completes their final study visit.

SELECTION AND WITHDRAWAL OF PARTICIPANTS

Recruitment

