15 participants will be recruited from the Renal Dialysis Unit at the Royal Derby Hospital. Potential participants will be approached by the clinical care team (which may include members of the research team) with reference to the inclusion and exclusion criteria. Each eligible participant will be given a Participant Information Sheet (PIS) and a minimum of 24 hours to consider whether they wish to participate in the study. At this time, the PIS will be discussed with them, any questions answered, and informed consent will be obtained by one of the investigators if they are willing to enter the study.

It will be explained to the potential participant that entry into the study is entirely voluntary and that their treatment and care will not be affected by their decision. It will also be explained that they can withdraw at any time. In the event of their withdrawal, it will be explained that their data collected so far cannot be erased and we will seek consent to use the data in the final analyses where appropriate.

If needed, the hospital interpreter and translator services will be available to assist with discussion of the study, the PIS, consent form, and be available for the duration of the study if required. The consent form and PIS will not be available printed in other languages.

Eligibility criteria

Inclusion criteria:

- CRP level >5.0 mg/L.
- Age: ≥ 18 years (no upper age limit).
- At least three haemodialysis sessions per week for ≥ 3 hours using a biocompatible dialyser.
- Able to give informed consent.

Exclusion criteria:

- Treatment with drugs that cause immunosuppression.
- Non-English speakers or those with special communication needs.
- Pregnancy, breast feeding or intending pregnancy.
- Expected survival <6 months.
- Hospitalisation at the time of screening.
- Known intolerance or allergy to ONS (or isolated ingredients).
- Pre-dialysis serum potassium >5.0 mmol/L.
- Unable to provide informed consent.

Participant Withdrawal

Participants will be withdrawn from the study if they:

- Withdraw their consent at any time.
- Become pregnant.
- Receive a kidney transplant.
- Do not adhere to the intervention; defined as $<50\%$ of the provided immuno-nutrition supplement being consumed.

Participants do not have to provide a reason for withdrawal of consent. Participants will also be withdrawn if it is deemed unsafe or is found to be impossible to proceed in the opinion of the investigators.

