Participants may be withdrawn from the study either at their own request or at the discretion of the Investigator. The participants will be made aware that this will not affect their future care. Participants will be made aware (via the PIS and consent form) that should they withdraw the data collected to date cannot be erased and may still be used in the final analysis.

Participants will not be replaced if they withdraw from the study.

Informed consent

The process for obtaining participant informed consent will be in accordance with the Research Ethics Committee (REC) guidance, Good Clinical Practice (GCP) and any other regulatory requirements that might be introduced. The investigator or their nominee and the participant shall both sign and date the consent form before the person can participate in the study.

The participant will receive a copy of the signed and dated consent form and the original will be retained in the Study records. A second copy will be filed in the participant's medical notes and a signed and dated note made in the notes that informed consent was obtained for the study. The decision regarding participation in the study is entirely voluntary. The investigator or their nominee shall emphasize to them that consent regarding study participation may be withdrawn at any time without penalty or affecting the quality or quantity of their future medical care, or loss of benefits to which the participant is otherwise entitled. No study-specific procedures will be done before informed consent has been obtained.

The investigator will inform the participant of any relevant information that becomes available during the course of the study and will discuss with them whether they wish to continue with the study. If applicable they will be asked to sign revised consent forms.

If the consent form is amended during the study, the investigator shall follow all applicable regulatory requirements pertaining to approval of the amended consent form by the REC and use of the amended form (including for ongoing participants).

STUDY REGIMEN

Once participants have given their informed consent, they will be advised to take **daily** one sachet (74 g) of the immuno-nutrition supplement (Oral Impact®, Nestle) dissolved in 125 ml of water and will be followed-up for 6 weeks.

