Participants will receive individualised (to patient needs and food preferences) dietetic advice formulated and delivered by an experienced renal dietitian under an honorary NHS research contract ([name]), who is a member of the research team and will be supervised by an NHS renal dietitian, aiming to achieve estimated nutritional requirements for people on haemodialysis (i.e., energy: 30-35 kcal/kg/day, and protein intake: 1.0-1.2 g/kg/day) [23]. Each dietetic advice provided to participants will also be reviewed by the NHS clinical renal dietitians who are members of the participants' usual clinical care team.

Consumption of the immuno-nutrition supplement will be supervised during haemodialysis sessions (thrice weekly) and self-reported (written and counting empty sachets) on non-dialysis days. Participants will receive precise oral instructions on how and when to take the supplement with close monitoring by the renal dietitian on the research team to encourage adherence to the intervention.

Three-day food diaries (i.e., one dialysis day, one non-dialysis day and one weekend day) will be completed by the participants at baseline, 3 and 6 weeks of follow-up, and will be analysed (Microdiet, Downlee Systems Ltd, UK) to assess compliance with the advice provided and to assess energy, protein and fat intake across the study period.

Data collection procedures

Hospital electronic medical records will be used to collect relevant baseline participant characteristics, including age, sex, ethnicity, time since dialysis initiation, dialysis adequacy,

current medication, presence of diabetes and history of cardiovascular disease. Information regarding educational level, occupation status, and history of smoking will be obtained by direct interview with the participants at the time of the baseline assessment. A blood sample will be taken weekly pre-dialysis after commencing the immuno-nutrition supplement to monitor serum potassium. Results from routine clinical blood tests will be recorded at baseline and 6 weeks of follow-up and will include haemoglobin, urea, creatinine, potassium, phosphate, calcium, sodium, albumin, total proteins, total cholesterol, triglycerides and CRP.

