Blood samples will be taken at the Renal Dialysis Unit and transferred to the local NHS laboratory (which is serviced and managed according to national UKAS standards and governance frameworks) at the Royal Derby Hospital for routine biochemistry and

haematology testing. These samples will be labelled according to NHS requirements. No DNA or RNA extraction will occur as part of this study.

STATISTICS

Statistical analyses will be performed using SPSS version 28.0. Data will be presented as mean \pm standard deviation, median (interquartile range), or percentages, as appropriate. To compare baseline versus final evaluations, a Wilcoxon test or paired t-test will be used in the case of dimensional variables, and McNemar test in the case of categorical variables. Intergroup comparisons will be performed using Mann-Whitney test or Student t-test for continuous variables and χ^2 test or Fisher's exact test for categorical variables. An alpha error of less than 0.05 will be judged to be significant. All data will be analysed on University of Nottingham computers and backed up regularly.

Sample size and justification

A formal power calculation is not appropriate for this pilot study design, and consequently, the sample size has been selected on a pragmatic basis. We will aim to recruit 15 participants in total.

Procedures for missing, unused and spurious data

All missing data will be explained. If a space on the Case Report Form (CRF) is left blank because the procedure was not done or a question was not asked, "N/D" will be recorded. If the item is not applicable to the individual case, "N/A" will be recorded. All entries will be printed legibly in black ink. If any error is made in data entry, to correct the error, a single straight line will be drawn through the incorrect entry and the correct data entered above it. All such changes will be initialled and dated. Errors will not be erased or altered by any other method. For clarification of illegible or uncertain entries, the clarification will be printed above the item, initialled and dated. Correction fluid will not be used.

Definition of populations analysed

The study will analyse the following populations:

- Safety set: All participants who underwent at least one study session.
- Full Analysis set: All participants, who participated in at least one study session and for whom at least one post-baseline assessment of the primary endpoint is available.

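### Eligibility and baseline potassium are not kept apart; if one routine result serves as both, the 6-week change in potassium is biased upward

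*Combined protocol and SAP*

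**What the plan says.** - **Entry.** The exclusion criteria, in the synopsis and again under Selection and Withdrawal of Participants, include "Pre-dialysis serum potassium >5.0 mmol/L". Under Recruitment, the clinical team approaches people by reference to the criteria, and those who are eligible receive the information sheet. Under Informed consent, "No study-specific procedures will be done before informed consent has been obtained".
- **Endpoints.** Under Study Configuration, the secondary endpoints are changes after 6 weeks, and the first group is "Biochemical blood variables including haemoglobin, urea, creatinine, potassium, phosphate, calcium, sodium, albumin, total proteins, total cholesterol and triglycerides". The safety endpoints include "Monitoring of pre-dialysis serum potassium levels", with no change from baseline, threshold or test attached.
- **Sampling.** Under Data collection procedures, "Results from routine clinical blood tests will be recorded at baseline and 6 weeks of follow-up", and potassium is on that list. The study's own potassium sampling comes later: "A blood sample will be taken weekly pre-dialysis after commencing the immuno-nutrition supplement to monitor serum potassium".
- **Design and analysis.** "This will be a single-centre, non-randomised, interventional pilot study". Under Statistics, "To compare baseline versus final evaluations, a Wilcoxon test or paired t-test will be used in the case of dimensional variables", with significance judged at 0.05.

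The documents do not say which potassium result decides eligibility, how old it may be, or whether baseline must be a different sample.

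**The concern.** The plan selects people on potassium and then measures change in potassium. Because nothing study-specific may be done before consent, an eligibility check made beforehand has to use a result already on file. Baseline potassium is also read from routine results. Using the same result twice is therefore compatible with the plan, and it is the easiest course.

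A value that had to be 5.0 mmol/L or lower will, on average, understate the person's usual level. The next reading then tends to be higher whatever was given in between. In a one-group before-after comparison this selection effect looks the same as a treatment effect.

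The direction matters because Appendix 1 lists 402 mg (10 mmol) of potassium per sachet and the regimen is one sachet daily, so a rise would readily be put down to the supplement. Dietetic advice is given alongside, and no control group is available to separate the explanations. The background section says the pilot's findings will help design a randomised trial, so a spurious rise could carry over into that planning.

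**Working it through.** **Is there a figure to reproduce?** No. The sample size of 15 is pragmatic, and the documents state no power, effect size, SD or expected potassium value.

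**Inputs from the documents:** upper cut-off c = 5.0 mmol/L; n = 15; one group; paired baseline-versus-final test; alpha 0.05 (taken as two-sided, since sidedness is not stated).

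**Assumed inputs, not in the documents:** potassium normally distributed in the dialysis unit, mean 4.6 to 5.2 mmol/L, SD 0.6 to 0.8 mmol/L, correlation rho between two occasions in the same person 0.4 to 0.8, and no supplement effect.

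**Case A: the qualifying value is the baseline.** For a normal variable truncated above at c, the expected rise at the next measurement is

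drift = (1 − rho) × SD × φ(a)/Φ(a), with a = (c − mean)/SD,

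where φ and Φ are the standard normal density and distribution function.

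- Low end (mean 4.6, SD 0.6, rho 0.8): a = 0.4/0.6 = 0.667; φ/Φ = 0.319/0.748 = 0.427; drift = 0.2 × 0.6 × 0.427 = **+0.05 mmol/L**.
- Mid case (mean 5.0, SD 0.7, rho 0.6): a = 0; φ/Φ = 0.399/0.5 = 0.798; drift = 0.4 × 0.7 × 0.798 = **+0.22 mmol/L**.
- High end (mean 5.2, SD 0.8, rho 0.4): a = −0.2/0.8 = −0.25; φ/Φ = 0.387/0.401 = 0.964; drift = 0.6 × 0.8 × 0.964 = **+0.46 mmol/L**.

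Simulated trials analysed with the paired t-test gave the same drifts and these rates of significance with no true effect:

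| Mean, SD, rho | Drift (mmol/L) | Completers | Significant |
|---|---|---|---|
| 4.6, 0.6, 0.8 | +0.05 | 15 | 8% |
| 5.0, 0.7, 0.6 | +0.22 | 15 | 28% |
| 5.0, 0.7, 0.6 | +0.22 | 12 | 23% |
| 5.0, 0.7, 0.6 | +0.22 | 10 | 19% |
| 5.2, 0.8, 0.4 | +0.46 | 15 | 58% |
| 5.2, 0.6, 0.4 | +0.37 | 15 | 63% |

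Nearly all the significant results are rises. The highest error rate does not fall in the row with the largest drift, because the smaller SD makes the test more sensitive.

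**Case B: baseline is a separate sample.** Selection then affects baseline and final values equally. Across the whole assumed grid the simulated drift was −0.005 to +0.004 mmol/L and the two-sided rejection rate 4.5% to 5.5%, which is nominal.

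**Case C: separate sample, but people above 5.0 on it are dropped.** In the mid case about 30% of new baselines would exceed 5.0 by ordinary variation. Dropping them truncates the baseline again: drift +0.16 mmol/L, with about 16% of trials falsely significant. A separate sample therefore helps only if it is not used to choose who is analysed.

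**The case against.** The strongest reply is that the documents never say the qualifying value is the baseline, and parts of them point to a fresh sample. At least 24 hours pass between the information sheet and consent. Data collection refers to a distinct baseline assessment. A pre-dialysis blood draw is planned at baseline. Laboratory Analyses describes samples taken at the unit for routine biochemistry. This stands as far as it goes. A reader might infer that potassium will drift upward in this study, and the documents do not support that: the bias is conditional on reuse, and even then it is an expectation, not a certainty in 15 people. But the documents do not require a fresh potassium sample either. The baseline draw is described for plasma cytokines, and weekly potassium sampling starts only once the supplement has begun.

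A reader might also infer that the safety endpoint is biased. It is defined as monitoring of levels, so the bias reaches it only where weekly values are read against the qualifying value. Likewise, the share of people with at least one of six weekly values above 5.0 (about 29% to 89% over the assumed ranges, with no supplement effect) is the same whichever baseline is used and is not part of this defect.

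Two further points stand. The size cannot be derived from the documents, and its lower end is close to negligible. The documents also contain no rule by which a rise in potassium would lead to the supplement being declared unsafe, and potassium is one of eleven named biochemical variables. A wrong safety conclusion is a risk of interpretation, not a planned decision.

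**Conclusion.** The point holds in conditional form. The plan leaves the eligibility value and the baseline value for potassium unseparated. If one routine result serves both purposes, the secondary endpoint of 6-week change is biased upward, as is any comparison of weekly values with that baseline, and a single-arm design cannot reveal it. With no supplement effect and n = 15, the bias is +0.05 to +0.46 mmol/L and the false-significance rate 8% to 63% against a nominal 5%; the mid case is +0.22 mmol/L and 28%, or 19% with 10 completers. These figures rest on normality and on assumed means, SDs and correlations that the documents do not supply. The direction does not depend on the exact values, provided the correlation between occasions is below 1. The matter is confined to one secondary variable in a small pilot, but it is cheap to settle before recruitment.

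**What to change.** 1. State under Data collection procedures and Statistics that baseline potassium for the change analysis is a pre-dialysis sample taken after eligibility is confirmed and before the first sachet, and that the qualifying result is not used as baseline. The planned baseline venepuncture can serve. Because that draw is described for frozen plasma, an extra tube to the NHS laboratory may be needed.
2. State that the analysed group is not re-selected on this sample, since dropping people on it would bring the truncation back. How a value above 5.0 mmol/L on it relates to the eligibility criterion is for the sponsor to reconcile in the text.
3. Show each participant's earlier routine pre-dialysis potassium values, with the qualifying value marked, beside the weekly on-study values. This gives the untreated spread against which weekly levels can be read.

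The cost is a short addition to the text, one routine assay for each of 15 participants and a look-up in the electronic record. The change removes the selection bias from the change endpoint. It does not separate a supplement effect from a dietary one, which a single-arm design cannot do.
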